- **Neurologic:** Dizziness, lightheadedness, abnormal dreams (more vivid dreams, • nightmares, etc.), and possibly hallucinations (rare) during the first 30 days following initiation of an ART regimen that contains the NNRTI efavirenz (EFV) **[NOTE:** We will report when grade 2 or higher or deemed "clinically significant" by study team personnel]. Renal: The integrase strand inhibitor dolutegravir (DTG) will be coming into wide use for first line ART regimens (and other subsequent ART regimen lines) in Nigeria during the study period (2019), pending final safety data, consistent with the WHO directive for wide-scale implementation of Tenofovir. Lamivudine, plus Dolutegravir (TLD) for first-line ART, given it considerably more favorable genotypic drug resistance profile (i.e. significantly higher genetic barrier for resistance to develop) and tolerability profile. Of note, DTG induces a noticeable increase in serum creatinine following initiation of therapy due to nonpathologic tubular blockade of creatinine secretion through the inhibition of OCT2.¹³⁰ DTG can block the tubular uptake of creatinine from the blood, leading to increases in serum creatinine and decreased eGFR or creatinine clearance (Cr CI), without changing the true GFR.¹³⁰ Therefore, based on published literature, an anticipated change in renal parameters is expected in study participants shortly after switching to DTG-based therapy. Specifically, patients switched to dolutegravir (from efavirenz or nevirapine) may experience a sustained increase in their serum creatinine coupled with a corresponding decrease in their calculated In brief, for a period of up to 48 weeks following dolutegravir (DTG) eGFR.

initiation, it is anticipated that study participants may experience a modest (0.2 mg/dL) increase in serum creatinine¹²⁷⁻¹²⁹ that will not lead to significant changes in uACR values but will lead to aim 2 study participants having a "new baseline eGFR" that is unrelated to study medication and based on the literature using iohexol ¹³⁰ will not represent a true change in eGFR; but nonetheless will still need to be accounted for in the analysis plan. **NOTE**: Given the known limitations of CysC-based equations for HIV-positive individuals, from an analysis standpoint, the team will utilize/rely on significant changes in serum creatinine (sCr) for safety monitoring/reporting among DTG-treated study participants.

Non-Reportable Events

Please see above "Anticipated AEs" section as the R3 study does not have any non-reportable events, other than these mild potential side effects (grade 1 only).

Reporting of SAEs and Unanticipated Problems

Study sites are required to report SAEs in REDCap to the R3 SOC and SSC within 24 hours of first knowledge of the event. To report such events, an SAE form will be completed by the investigator and faxed or emailed to the SOC/SSC. The SOC/SSC will facilitate the timely medical review and reporting of the event and provide reports to the NIDDK and the Data and Safety Monitoring Board (DSMB) in accordance with DSMB-approved study policies and regulatory requirements. All AEs will be reviewed within 48 hours, and an appropriate course of action will be determined. All study staff will also be encouraged to report any SAEs directly to the SOC and SSC by phone or direct email, as it is essential that they are notified with 24 hours of the study team member learning of the event.

Any/all grade 3 (i.e. grade 3 = "severe"; grade 4 = "life-threatening" and grade 5 = "death"), grade 3 or higher events deemed "*definitely related to study medication*" or "*possibly related to study medication*", and/or unanticipated adverse events will be reported to both IRBs (VU and AKTH), NIDDK, and the DSMB within 48 hours of the site becoming aware of the event. Non-serious (grade 1 or 2) unanticipated AEs will be reported to both IRBs and NIDDK within as outlined on Table 3 below; namely internally reviewed/reported from the study site to the SOC/SSC on a monthly basis and submitted/reported to the involved IRBs and NIDDK on a quarterly basis. All unanticipated events will be reported to the chair of the DSMB and the NIDDK Program Officer within 48 hours. Any determination by either IRB that results in a temporary or permanent suspension of the study will be immediately reported to NIDDK and the DSMB (within 24 hours of receiving notice from the IRB). Please refer to "**Table 3: R3 Adverse Event Reporting Timeline**" for full/specific details).

The study leadership (i.e. the Vanderbilt-based SOC as well as on-site Co-Investigators and Research Coordinator) will keep a copy of the SAE form on file at the study site (AKTH). At the time of the initial report, the following information should be provided:

- Study identifier
- Participant ID number
- A description of the event
- Date of onset
- Current status

- Whether study treatment was discontinued
- The reason the event is classified as serious or unanticipated
- Investigator assessment of the "relatedness" between the event and study participation

Within the following 7 days, the investigator will provide the SOC and SSC further information on the SAE or the unanticipated problem in the form of a written narrative. This should include a copy of the completed SAE form, and any other diagnostic information that will assist in the understanding of the event. Significant new information on ongoing SAEs should be provided promptly to the SOC/SSC.

If a participant becomes pregnant while participating in R3 will be reported as an AE and will trigger the collection of additional documentation about the pregnancy including the immediate unblinding of the participant and discontinuation of study medication (lisinopril) if they were randomized to the active /intervention arm. Pregnancy outcomes will be collected, including the outcome of the infant and if the pregnancy was terminated. This information will be submitted to the Vanderbilt University IRB, the AKTH (study site) IRB, and NIDDK (study funder---who will forward this along to the DSMB), as required.

SAEs that are still ongoing at the end of the study period must be followed up to ascertain the definitive outcome. Any SAEs that occur after the study period (up to 3 months post-study completion) and is considered to be "possibly related" to study treatment or study participation should be recorded and reported immediately.

Investigator Reporting to the IRB

Site investigators will report SAEs and Unanticipated events to their IRB in accordance with the reporting requirements of the local IRB or with the Office of Human Research Protections (OHRP) guidelines, whichever is sooner. OHRP recommends that:

- ALL unanticipated events (regardless of grade) that are "definitely related", "possibly related" or "unable to assess relatedness to study medication" should be reported to involved IRBs and NIDDK within 48 hours of the investigator becoming aware of the event;
- ALL serious adverse events (SAEs) that are unanticipated (regardless of *"relatedness"* to study medication") should be reported to involved IRBs and NIDDK within 48 hours of the investigator becoming aware of the event

Type of Event / Body being reported to	Anticipated Events (Grades 3 & 4) ["definitely related" OR "possibly related" to study medication]	Unanticipated Events (Grades 1 & 2) ["definitely related", "possibly related" OR "unable to assess relatedness" to study medication]	Unanticipated Events (Grades 3 & 4) ["definitely related", "possibly related", OR "unable to assess relatedness" to study medication]	Other Reportable Events* [regardless of "relatedness"] [Grade of Event "Not Relevant"]	Any Grade 5 Event [regardless of "relatedness"]
Involved IRBs (VU and AKTH)	Aggregate reporting on a quarterly basis	Aggregate reporting on a quarterly basis	Within 48 hours of site becoming aware of event	Within 48 hours of site becoming aware of event	Within 48 hours of site becoming aware of event
NIDDK (DSMB)	Aggregate reporting on a quarterly basis	Aggregate reporting on a quarterly basis	Within 48 hours of site becoming aware of event	Within 48 hours of site becoming aware of event	Within 48 hours of site becoming aware of event
AKTH Study Team	Aggregate review/internal reporting (to SOC/SSC) on a monthly basis	Aggregate review/internal reporting (to SOC/SSC) on a monthly basis	Notify SOC and SSC within 24 hours	Notify SOC and SSC within 24 hours	Notify SOC and SSC within 24 hours

 Table 3: R3 Adverse Event Reporting Timeline

* Other reportable events include the following:

- 1. Any AE that causes SOC to modify protocol/informed consent or prompt other action by IRB to assure patient protection
- 2. Breach of confidentiality
- 3. Change to the protocol made without prior IRB review to eliminate apparent immediate hazard to a research participant
- 4. Complaint of a participant that indicates unanticipated risks, or the complaint cannot be resolved by the study team
- 5. Protocol violation

Reporting Process

Unanticipated problems posing risks to participants or others as noted above will be reported using the appropriate IRB-designated form or as a written report of the event (including a description of the event with information regarding its fulfillment of the above criteria, follow-up/resolution and need for revision to consent form and/or other study documentation).

Copies of each report and documentation of IRB notification and receipt will be maintained in the AKTH Study Site Investigator's study file.

Other Reportable Events (please also refer to LEGEND/FOOTNOTE at the bottom of Table 3):

- Any AE that would cause the R3 SOC to modify the protocol or informed consent form or would prompt other action by the IRB to assure protection of human participants. Information that indicates a change to the risks or potential benefits of the research, in terms of severity or frequency.
- Breach of confidentiality.
- Change to the protocol made without prior IRB review to eliminate apparent immediate hazard to a research participant.
- Complaint of a participant when the complaint indicates unexpected risks, or the complaint cannot be resolved by the research team.
- Protocol violation (meaning an accidental or unintentional deviation from the IRB approved protocol) that in the opinion of the investigator placed one or more participants at increased risk or affects the rights or welfare of participants.
- **NOTE:** Any/all study events meeting "**Other Reportable Events**" criteria as outlined above should be reported to involved IRBs and NIDDK within 48 hours of the investigator becoming aware of the event.

SSC Notification to Participating Study Investigators

The R3 SCC will notify all on-site (AKTH-based) senior study leadership and the SOC, in a written safety report, of any AE that meets the criteria of an "unanticipated event" and/or AE "*definitely related to study medication*" or "*possibly related to study medication*" as described previously. The SOC will be responsible for notifying relevant other parties, including the Data and Safety Monitoring Board (DSMB), NIDDK, and involved IRBs.

Medical Monitoring

AKTH-based Co-Investigators and Research Coordinator will be responsible for overseeing the safety of the study at their study site. This safety monitoring will include careful assessment and appropriate reporting of AEs as noted above, as well as the implementation of a site data and approved Data Safety Monitoring Plan. Medical monitoring will include a regular assessment of the number and type of serious and/or unanticipated AEs.

C. Safety Monitoring Plan

All AEs will initially be reviewed (after being sent from the on-site study team) and categorized by the study Program Manager and then by the SOC and SSC (when relevant; i.e. the SSC is involved), according to the timeline as outlined above in "Table 3: R3 Adverse Event Reporting Timeline". Weekly meetings with the study team will also look at overall statistics for AEs. Reports that include AEs will also be sent to NIDDK and the Chair of the DSMB on a quarterly basis for review and dissemination to other DSMB members (as specified above in "Table 3: R3 Adverse Event Reporting Timeline").

Study progress (including recruitment, consent procedures, retention, laboratory results, and protocol adherence measures) will be reviewed on a **weekly** basis by the study team leadership at VUMC and on-site at AKTH.

Quarterly reports sent to NIDDK and the DSMB will include a list and summary of AEs, determination of whether these AE rates are consistent with pre-study assumptions (i.e. anticipated or unanticipated, etc.), a summary of recruitment and retention, as well as a summary of reasons for loss-to-follow-up, and whether the study is on track with respect to the original timeline and proposed milestones.

Given the long recruitment period, the sample size, and the relatively short followup period, we will not have stopping rules for this trial. We will perform interim analyses at six months after enrollment into Aim 2 begins or after 50% enrollment into Aim 2 (n=70/arm, n=140 total) occurs to evaluate safety/toxicity and efficacy. These results will be shared with the DSMB and all relevant parties.

D. Informed Consent

Informed consent will be obtained from each participant at entry into Study Aim 1, and again for those who proceed to Aim 2 (a subset of the participants from Aim 1). Informed consent will be collected in REDCap by trained study coordinators, who will provide a study information form and review the study consent form with the participant in the participant's language of preference (form will be available in both English and Hausa). The consent form will include all potential study risks and will be approved by both IRBs (Vanderbilt and AKTH). Forms will be uploaded through the central secure study database, housed at Vanderbilt.

E. Data Quality and Management

Study data will be collected in REDCap. Form fields, where possible, have include restrictions on data input (numeric fields restricted to possible ranges, text fields prevented from allowing numeric entries, etc.) to make data entry less prone to errors and prevent false outliers. Data cleaning and preparation for analysis will be ongoing, with consent forms and study data reviewed monthly or more frequently. Data management and data quality will be regularly reviewed by the study team

leadership (Multiple-PIs, Study Manager, and on-site AKTH study leadership). The study leadership will also provide results to the DSMB in twice-yearly reports.

F. Confidentiality

Study participants will be assigned a coded identification number at the time of study registration. In order to maintain patient confidentiality, all laboratory specimens, study case report forms, and reports will be identified using that coded number. Only research staff will have access to the coded number. Key study personnel including Dr(s). [name] and [name] (MPIs), [name], [name], [name], [name], [name], [name], and [name] will store research data including medical and laboratory records in locked cabinets and all e-files will be password protected. Data will be stored in password-protected files within secure buildings at AKTH and VUMC. We have additional measures to enhance security when data are housed at Vanderbilt. Access to all data will be ID and password-protected, including data warehouse software and computers managing and analyzing survey data. Clinical information will not be released without the written permission of the participant. No data will be released with any information that may directly or indirectly identify participants, their clinical information, or laboratory results to outside agencies.

The data gathered will be entered into the research electronic data capture (REDCap) data system, with each ID having a unique identifier for each participant. REDCap is a secure, web-based application for building and managing online databases. All data will be de-identified and samples will only have a unique identifier that will link the unique identifier with the patient's name. REDCap is a free, secure, web-based application designed to support data capture for research studies. The system was developed by a multi-institutional consortium initiated at Vanderbilt University. Data collection is customized for each study or clinical trial by the research team with guidance from Harvard Catalyst EDC Support Staff. REDCap is designed to comply with Health Insurance Portability and Accountability Act (HIPAA) regulations. REDCap provides user-friendly webbased case report forms, real-time data entry validation (e.g. for data types and range checks), audit trails, and the ability to set up a calendar to schedule and track critical study events such as blood-draws, participant visits, etc. Also, designated users can assign different levels of access for each member of the research team.

REDCap and REDCap Survey (RS), as hosted by Vanderbilt, are available only to investigators from Vanderbilt University but can be used by investigators at other institutions as long as they are part of a project/group from Vanderbilt that is utilizing REDCap. REDCap and RS as software applications can be used at other institutions, when installed by and hosted at those institutions, if they are willing to sign a technology transfer agreement and join the REDCap Consortium. Investigators and research staff at AKTH are very comfortable with using REDCap, as [name] ongoing research studies there all utilize REDCap for data management.

The REDCap clinical database will be maintained by the Vanderbilt Institute for Global Health under the direction of the MPIs. The study team members are trained in HIPAA privacy regulations and other applicable site privacy policies. No information will be released, nor will participation in the research be acknowledged, to any party except where compulsory according to law or intuitional policy.

G. Data and Safety Monitoring Board (DSMB)

The information provided in this section of the protocol is a general description of the DSMB responsibilities and processes.

A DSMB has been established by the NIDDK and provides input to the study team. The DSMB is comprised of individuals with expertise in clinical trials design and methodology, biostatistics, clinical nephrology and other relevant medical specialties. The DSMB members are not affiliated with the study and are appointed by the NIDDK. DSMB members will be free of conflicts of interest that could be affected by the outcomes of the study. During the study, DSMB members who develop real or perceived conflicts of interest that impact objectivity will disclose them to NIDDK project officers, who will arrange for replacement of the member, if indicated.

The DSMB will review the protocol before initiation of the study. After initial approval and during the course of the study, the primary responsibilities of the DSMB will be to:

- Review safety data and provide input to protect the safety of the study participants;
- Provide input on major changes to the research protocol and plans for data and safety monitoring;
- Provide input on the progress of the study, including periodic assessments of data quality and timeliness, participant recruitment, accrual and retention, participant risk versus benefit, performance of the study sites, and other factors that may affect study outcomes;
- Consider factors external to the study when relevant information becomes available, such as scientific or therapeutic developments that may have an impact on the need for continuation of the study, safety of the participants or the ethics of the study;
- Provide input on modification of the study protocol or possible early termination of the study because of attainment of study objectives, safety concerns, or inadequate performance (such as enrollment and retention problems).

The DSMB will review study data reports, including primary endpoint analyses, at a minimum of every six months either in a meeting or on a conference call.

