	baseline (Repeat ScR and monitor	1 week and monitor closely for signs of worsening kidney function
	closely for signs of worsening kidney	
	function; i.e. decreased urinary output,	eGFR worsens by 20-29% when compared
	fatigue, palpitations, dyspnea,	to baseline (Repeat eGFR within 1 week and
	lightheadedness, and/or generalized	monitor closely for signs of worsening kidney
	fatigue/malaise). If repeat sCr normalizes	function; i.e. decreased urinary output, fatigue,
	(< 1.2x below baseline value)	palpitations, dyspnea, lightheadedness, and/or
	(ESCALATE)	generalized fatigue/malaise). If repeat eGFR
		improves/normalizes (i.e. is reduced < 20%
	NOTE: Any time sCr increase 1.3 -1.8x	when compared to baseline) (ESCALATE)
	the upper limit of normal (ULN) OR sCr	
	increases between 1.3 - 1.49x from	NOTE: A 10-20% decrease in eGFR in
	baseline; this constitutes a grade 2 event.	baseline constitutes a grade 2 event; and
	Any time sCr increase 1.8 – 3.49x the	when any patient experiences a > 10% decline
	ULN OR sCr increases between 1.5 –	in eGFR (from baseline), their renal function
	1.99x from baseline; this constitutes a	needs to be more intensively monitored. A
	grade 3 event (and requires an SAE to be	decrease in eGFR between 30-50% (from
	completed)	baseline) constitutes a grade 3 event (and
	Anytime sCr increases by ≥ 1.3-fold;	requires an SAE to be completed)
	immediately HOLD study medication;	Anytime eGFR diminishes by > 30% from
	look for other possible	baseline; immediately HOLD study
	etiologies/contributing factors; and monitor	medication; look for other possible
	closely; repeating BMP within 1 week; If	etiologies/contributing factors; and monitor
	repeat sCr normalizes (< 1.2-fold below	closely; repeating eGFR within 1 week; If
	baseline value) (ESCALATE); but if sCr	repeat eGFR improves/normalizes (< 20%
	elevations persist by ≥ 1.3-fold from	below baseline value) (ESCALATE); but if
	baseline; continue to HOLD study	eGFR reductions persist by ≥ 30% from
	medication; involve the SOC/SSC; as	baseline; continue to HOLD study
	study medication may need to be	medication; involve the SOC/SSC; as study
	discontinued and AE report done	medication may need to be discontinued
	NOTE: All study participants resolution	and AE report done
	NOTE: All study participants receiving dolutegravir (DTG)-based ART may	Any study participant experiencing a drop
	experience a sustained increase in serum	in eGFR (at any time) to < 50 ml/min/1.73m ²

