	creatinine (sCr) (up to 0.2 mg/dL) that	(using CKD-EPI-Cr-CyC equation);
	may persist for up to 48 weeks (or	immediately HOLD study medication; look
	possibly longer) so to account for these	for other possible etiologies/contributing
	potential modest changes in renal	factors; and monitor closely; repeating eGFR
	function, all safety events involving kidney	within 1 week; involve the SOC/SSC; as
	function deemed "possibly" or "definitely	study medication may need to be discontinued
	related" to study medication among DTG-	and AE report done
	treated study participants will be	
	evaluated and graded using serum	
	creatinine (sCr) measurements.	
Step 2 to 3	Same as above for Step 1	Same as above for Step 1
(10 mg/d		
20 mg/u)		

Step 23to 4 (20 mg/d ↑ to 40 mg/d)	Same as above for Step 1	Same as above for Step 1

Risks of prescribed combination antiretroviral therapy (ART) (specifically tenofovir (TDF):

All eligible/enrolled aim 2 study participants will be receiving ART for 6+ months, and we anticipate that a significant proportion (i.e. > 80%) of them will be receiving tenofovir (TDF)-based regimens. We mention this because of the potential adverse events that have been attributed to the nucleotide reverse transcriptase inhibitor TDF, namely kidney toxicity which may manifest as a reduction in eGFR. These potential TDF-associated kidney manifestations that include reduced eGFR, Fanconi's syndrome, etc. are due to tubular (rather than glomerular) insults; and they often present within the first 1-2 years following TDF initiation and based on our preliminary analysis of enrolled aim 1 study participants (January 2019), the majority of aim 1 study participants (from which we will be screening/enrolling for aim 2) have been receiving ART for considerably longer periods of time (i.e. mean duration of ART > 8 years).

Management of Worsening Renal Function Among Study Participants receiving tenofovir (TDF)-based ART regimens:

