participant's calculated eGFR drops < 50 ml/min per 1.73m², the team will need to complete an AE report (send to the SOC/SSC) and update as needed. At this level of kidney function decline (< 50 ml/min per 1.73m²), the study participant's study medication needs to be immediately held and the patients need to be thoroughly evaluated for other potentially contributing causes of worsening kidney function; i.e. volume contraction (dehydration, sepsis, GI bleeding, etc.), obstruction, nephrotoxin (any potentially nephrotoxic medication (i.e. aminoglycosides, etc.), IV contrast, traditional medicines, etc.), and/or other causes (rhabdomyolysis, etc.). During this time of study medication hold, the participant needs to be monitored closely and have their blood pressure, electrolytes (specifically their K+), and kidney function (serum creatinine and calculated eGFR) monitored as deemed necessary by the study team in consultation with the SOC/SSC. Patients will need to have their eGFR reevaluated within 7 days (or sooner at the discretion of the treating clinician). If their eGFR has not stabilized/improved, with no other apparent etiology for worsening kidney function, consider holding tenofovir (TDF)(if on TDF-based ART) and/or dose reducing study medication (on a case-by-case basis; also in close collaboration/communication with the SOC/SSC). Depending on the kidney function/other parameters (i.e. K+, etc.), the study participant may need to be switched to an alternative ART regimen (i.e. switch TDF to ABC) and continue to monitor; and if their study medication was dose reduced, the on-site team will continue to monitor them closely to determine next steps; i.e. permanently discontinue study medication and/or other medications or attempt to resume study medication and titrate up the dose as deemed appropriate.

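### At eGFR below 50, the renal management text allows a reduced dose of already-held study drug without recovery, while the titration table says to keep holding it

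*Combined protocol and SAP*

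**What the plan says.** The text is in section 6.0, part A, under management of worsening renal function in persons receiving tenofovir plus study medication. Once eGFR is below 50, the participant's "study medication needs to be immediately held", other causes are sought, and eGFR is rechecked within 7 days. If eGFR has not stabilized or improved and no other cause is apparent, the team is to "consider holding tenofovir (TDF)(if on TDF-based ART) and/or dose reducing study medication", case by case with the SOC/SSC. The text continues: "if their study medication was dose reduced, the on-site team will continue to monitor them closely", the next steps being permanent discontinuation or an attempt to resume and titrate up.

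The same subsection refers sites to the Dose Titration Algorithm for management details. That is the first of several tables numbered 3, and it is the one meant by Table 3 below. Its hold rules apply at any time, not only at titration visits. On the repeat test, its eGFR column covers the case where "eGFR reductions persist by ≥ 30% from" baseline, and its creatinine column the case where "elevations persist by ≥ 1.3-fold from" baseline. In both columns the instruction that follows is "baseline; continue to HOLD study" medication, with SOC/SSC involvement. A separate rule for eGFR below 50 says to hold, repeat within a week and involve the SOC/SSC, and adds that "study medication may need to be discontinued". It names no reduced dose.

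**The concern.** Dose reduction is offered for a drug that has already been stopped, and the condition for offering it is that kidney function has not recovered. For many of the same participants, Table 3 says the opposite. A site following both texts has no stated rule for which one governs.

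This is a matter of participant safety. A lower-dose restart would re-expose someone with unrecovered kidney function to an ACE inhibitor. Only participants on lisinopril carry that risk. Under section 4.0 the study physicians are blinded, so they cannot tell who those participants are when they decide.

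**Working it through.** **Inputs.** Entry eGFR is at least 60 (section 3.0, Aim 2 criteria). The renal management trigger is eGFR below 50 (section 6.0). Table 3's continue-to-hold thresholds are an eGFR fall of 30% or more, or creatinine at 1.3-fold or more. Its recovery thresholds after a hold are an eGFR less than 20% below baseline and creatinine below 1.2-fold. The plan gives no figure of its own to reproduce here.

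**Step 1: the two texts at the repeat test.**

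| Situation at recheck | Renal management text | Table 3 |
|---|---|---|
| eGFR fall still 30% or more | Reduced dose may be considered | Continue to hold |
| Creatinine still 1.3-fold or more | Reduced dose may be considered | Continue to hold |
| eGFR still below 50, neither of the above | Reduced dose may be considered | Hold, possibly discontinue; no reduced dose named |

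The first two rows are a conflict and the third is a mismatch. Table 3 does name a reduced dose where one is intended: its potassium column, at the step from 10 to 20 mg, allows re-initiation at 50% of the prior dose. The renal columns contain nothing similar.

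**Step 2: where the eGFR rules collide.** The fall is 1 − eGFR/baseline, so a fall of 30% or more means eGFR ≤ 0.70 × baseline. That limit reaches 50 when baseline = 50/0.70 = 71.4.

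| Baseline eGFR | Conflict at or below (0.70 × baseline) | Mismatch-only width below 50 | Fall at eGFR 49.9 |
|---|---|---|---|
| 60 | 42.0 | 8.0 | 16.8% |
| 65 | 45.5 | 4.5 | 23.2% |
| 70 | 49.0 | 1.0 | 28.7% |
| 75 | every value below 50 | none | 33.5% |
| 90 | every value below 50 | none | 44.6% |

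At 42 or below the conflict holds for every eligible baseline. The creatinine rule can add participants who fall inside the mismatch-only band.

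**Step 3: what a restart rule needs.** At baseline 60, a value 20% below baseline is 0.80 × 60 = 48. The 20% limit reaches 50 at baseline 50/0.80 = 62.5. For baselines from 60 up to 62.5, a participant can therefore be less than 20% below baseline and still be under 50, so a restart rule needs both eGFR conditions.

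**Step 4: dolutegravir.** Section 5.0 (Nigeria standard of care), Table 3 and the anticipated-events text in section 6.0 all expect a creatinine rise of up to 0.2 mg/dL that is not a true change in GFR. A rise of 0.2 alone gives 1.2-fold when baseline creatinine is 0.2/0.2 = 1.0 mg/dL, and a larger ratio below that. It gives 1.3-fold at 0.2/0.3 = 0.67 mg/dL. A strict creatinine test against the original baseline could therefore bar a participant for a non-pathological shift.

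**The case against.** The strongest reply is that the texts can be read together: Table 3's hold governs, and a lower dose is an option only where that hold does not apply. The later wording about attempting to resume drug, and the following paragraph on eGFR that keeps falling despite the hold, both suggest that drug may still be off. The step is only to be considered, case by case, with the SOC/SSC. Section 7.0 also lists a serious adverse event among circumstances requiring discontinuation, and Table 3 requires an SAE form for an eGFR decrease of 30–50%.

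Part of this stands. A reader might infer that a site could restart drug on its own authority. The documents do not support that, because the SOC/SSC must be involved. But Table 3 involves the same committees and still says to hold, and nothing in the renal management text confines dose reduction to cases outside that hold. Section 7.0 is generic, and its next sentence softens to possible modification or discontinuation. It favours holding but does not reconcile the two texts.

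Three stronger readings also go too far:

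- A reader might infer a direct contradiction at every eGFR below 50. For baselines from 60 to about 71.4, with a fall under 30% and creatinine under 1.3-fold, there is only a mismatch.
- A reader might see a similar conflict over tenofovir. Section 6.0 already makes a switch standard of care at eGFR 30–49, and the renal management text says "the study participant may need to be switched to an alternative ART regimen". No contradiction follows.
- A reader might use Table S7 to forecast how many participants are affected. Its treatment-arm rates are power scenarios for tenofovir toxicity defined by two renal criteria, not predictions for this step.

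**Conclusion.** The point holds as a conflict between two safety instructions and should be corrected. On the eGFR rule it covers all values below 50 for baselines of about 71.4 or more, and values at or below 0.70 × baseline for lower baselines. Persistent creatinine at 1.3-fold or more adds to this. The rest is a mismatch with Table 3's rule for eGFR below 50.

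The conclusion rests on reading dose reduction of a held drug as a restart. That is the only reading under which the instruction does anything, although the surrounding wording is muddled.

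The practical risk is limited. The step requires eGFR below 50, no improvement at recheck and no other cause, and it goes through the SOC/SSC. The documents give no expected number of participants. The effect on the albuminuria endpoints should be small: few participants are likely to meet all those conditions, and the primary analysis is by intention to treat. No power or type I error figure is affected.

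**What to change.** In the renal management text of section 6.0, replace the dose-reduction option with an instruction to continue holding study medication. Reword the later clause about drug that was dose reduced so that it refers to a reduced-dose restart after recovery. Permit that restart only when all of these are met:

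- the SOC/SSC have reviewed the case;
- section 7.0 has not required discontinuation;
- eGFR is less than 20% below baseline and no longer below 50;
- creatinine is below 1.2-fold of baseline.

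The 20% and 1.2-fold limits are Table 3's own recovery criteria. For participants switched to dolutegravir, have the SOC/SSC judge recovery with allowance for the expected creatinine rise of up to 0.2 mg/dL. No tenofovir edit is needed for this point.

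The cost is a protocol wording change and brief site retraining, with no added visits, tests or participants.
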